7.0 Data and Specimen Banking*

7.1 Data will be kept in password protected files on encrypted computers that only study staff will have access to.

7.2 The data stored will include demographics and all responses to self-report questionnaires. Subjects will be assigned an ID number. Data will not be linked to participants' names.

8.0 Sharing of Results with Subjects*

8.1 Individual or study results will not be shared with subjects directly.

9.0 Study Timelines*

9.1 Subjects will be in the study for 6 weeks total. We anticipate 1 year to enroll all study subjects.

10.0 Subject Population*

PROTOCOL TITLE: A Randomized Controlled Trial of an Exposure-Based Intervention for Perfectionism

- 10.1* Individuals (ages 18-65) from the psychology subject pool and the community will be recruited for the study.
- 10.2* The subject population will consist of individuals with high levels of perfectionism (based on scores on the Frost Multidimensional Perfectionism Scale). Subjects must be between the ages of 18 and 65 and score at least a 29 on the FMPS-CM. Exclusion criteria include currently being in psychotherapy and any changes to psychotropic medications in the past 4 weeks.
- 10.3* We will exclude the following populations:
 - Adults unable to consent
 - Individuals who are not yet adults (infants, children, teenagers)
 - Prisoners

11.0 Vulnerable Populations*

N/A

12.0 Local Number of Subjects

- 12.1* 84 subjects will be recruited, with 42 in the ETP group and 42 in the stress management group.

13.0 Recruitment Methods

- 13.1* Subjects will be recruited at Florida State University using the psychology subject pool and through the community using flyers and online advertisements.
- 13.2* Subjects will be identified using the mass screening survey. They may also respond to the posting on SONA, a flyer, or an online advertisement.
- 13.3* Questions from the FMPS will be used on the mass screening survey in order to recruit subjects. Study slots will be posted on SONA, which potential subjects can see if they are eligible to sign up for.

14.0 Withdrawal of Subjects*

- 14.1* Subjects may be withdrawn from the study without their consent if a risk arises that could harm the participant or others. For example, if a subject discloses intent to harm themselves or others, they may be withdrawn from the study.
- 14.2* When subjects withdraw from the research before the completion of the study, we will ask if they are willing to complete the post-test assessment.

15.0 Risks to Subjects*

- 15.1* The risks to human subjects in the proposed study are minimal. Nevertheless, precautions will be taken to minimize participants' risk in the study. All individuals will be informed of the nature of the investigation and the types of assessments and procedures. Participants will be given an opportunity to have any questions answered to their satisfaction and then will be asked to sign an informed consent statement prior to participating in the project. The specific potential risks involved in the proposed investigation are enumerated below.

PROTOCOL TITLE: A Randomized Controlled Trial of an Exposure-Based Intervention for Perfectionism

Self-report measures:

There are no foreseeable risks associated with these assessment procedures. While some participants may be hesitant to answer the assessment forms, others may derive benefit from the self-assessment as it could increase their awareness of the relationship between their symptoms and environmental, cognitive, and interpersonal factors. In addition, referrals to appropriate clinical services (e.g., ABHC, FSU Psychology Clinic) will be provided for any participants seeking intervention after the study. Phone numbers for these clinical services will be provided within the debriefing form, which will be available for participants to read on Qualtrics after completing the follow-up questionnaires.

Intervention risks:

The perfectionism intervention is exposure-based, which means that it is expected to involve some discomfort for the subject. The intervention may lead to distress for subjects. They are told that they may feel psychologically uncomfortable, but that it is expected during this intervention. Participants will be able to stop intervention at any time. The benefits of exposure-based interventions have shown that though anxiety-provoking, the distress is temporary and there is often symptom-relief both in the short and long-term. For the stress management condition, similar tasks have been used in previous research ([name] et al., 2017; Smith et al., 2018; Smith et al., 2019) and are very unlikely to cause any significant distress or discomfort.

General Protection Against Risks:

At their request, participants will be referred to clinicians with whom they may speak about their discomfort or distress.

Safeguards for maintaining confidentiality:

The confidentiality of all participants in this study will be maintained. Each participant will be assigned an Identification Code with which all questionnaires will be labeled. This Identification Code will be used as the participant's username for the study website. The information from the website will be secure and only accessible to study personnel. All answers to the participants' questions will be identified by the code number. Names will not appear on any of the results. No individual responses will be reported in any publications. All project staff and participants will be well informed about regulations pertaining to confidentiality. The link between subject and identification number will be destroyed following completion of the study. No records or assessment information will be released to any other person. No audio or videotapes will be used.

Safeguards for maintaining patient safety: Persons who express high risk symptomatology (e.g., suicidal ideation or other forms of serious threat to themselves or others) at any time they are in contact with the study personnel will receive ethically and legally appropriate courses of action. This would include assessment of seriousness of danger or disablement and referral for immediate crisis management (e.g., hotlines, crisis centers, hospitals, or contacting emergency psychiatric teams or police if necessary). Study personnel who have direct contact with study participants (e.g., scheduling staff) will be trained in methods of crisis

PROTOCOL TITLE: A Randomized Controlled Trial of an Exposure-Based Intervention for Perfectionism

management. A detailed step-by-step protocol will be available for dealing with such crises (see uploaded suicide risk procedures form).

In view of the safeguards detailed above, the possibility of a medical or psychological incident arising is remote.

15.2 This is a new intervention and thus may have unforeseeable risks.

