Sixteen days after the baseline visit, participants in both groups will be asked to complete the post-assessment questionnaires via a link that will be sent to them via email. One month after completing the post-test measures, they will be sent the same questionnaires to complete again. SONA participants will receive 3 credits after completing the post-test questionnaires and 1 credit after completing the follow-up questionnaires. Community participants will receive an Amazon gift card via email for \$10 after completing the post-test questionnaires and an additional Amazon gift card, delivered via email, for \$10 after completing the follow-up questionnaires.

PROTOCOL TITLE: A Randomized Controlled Trial of an Exposure-Based Intervention for Perfectionism

All participants will be debriefed after completing follow-up assessments.

After completing all assessments for the study, participants will be emailed to ask for feedback about the treatment. The text of the email will say:

“We are interested in your feedback on the treatment for perfectionism you received. What were your general impressions of the treatment? Were there parts of the treatment you would change to make it better? If so, what would you recommend?”

They may opt-out or not reply if they choose.

Questionnaires:

Frost Multidimensional Perfectionism Scale (FMPS; Frost et al., 1990)

Credibility and Expectancy Questionnaire (Borkovec & Nau, 1972)

Center for Epidemiological Studies Depression Scale (CES-D; Radloff, 1977)

Social Phobia Index (SPIN; Connor et al., 2000)

Generalized Anxiety Disorder-7 (GAD-7; Spitzer et al., 2006)

ED-15 (Tatham et al., 2015)

Irrational Procrastination Scale (IPS; Steel, 2010)

Massachusetts General Hospital Hair Pulling Scale (MGH-HPS; Keuthen et al., 1995)

Skin Picking Scale Revised (SPS-R; Snorrason et al., 2012)

6.3

- Participants who have previously completed ETP reported no adverse effects ([name] & [name], under review).
- To lessen the risks, participants will be explained what the conditions will look like and what the rationale behind it is before engaging in interventions.
- All data collection materials can be found in the appendix of the IRB submission.

6.4 Data collected during the study will be obtained via self-report from subjects. Data will include demographics and self-report questionnaire responses.

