18.0 Provisions to Monitor the Data to Ensure the Safety of Subjects*

N/A

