24.0 Setting

24.1 All baseline questionnaires and procedures, intervention sessions, post-test questionnaires, and follow-up questionnaires will take place outside of the lab online via Qualtrics.

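### Referral information is scheduled only after follow-up, and no unwanted-effects item or analysis of individual worsening is prespecified, although the protocol anticipates distress and possible unforeseen risks

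*Combined protocol and SAP*

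**What the plan says.** **Anticipated risk.** Section 15.1 rates the overall risk as minimal but says the ETP tasks are expected to be uncomfortable and can be distressing. Section 15.2 adds: "This is a new intervention and thus may have unforeseeable risks".

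**Referral information.** Section 15.1 puts the phone numbers of clinical services in the debriefing form, "which will be available for participants to read on Qualtrics after completing the follow-up questionnaires". Section 6.2 gives the same timing: "All participants will be debriefed after completing follow-up assessments".

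**Help before that point.** Section 15.1 states: "At their request, participants will be referred to clinicians with whom they may speak about their discomfort or distress". The crisis procedure in the same section covers people who express high-risk symptoms "at any time they are in contact with the study personnel". Section 22.1 gives everyone staff contact details before consent.

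**Withdrawal.** For those who leave early, section 14.2 says "we will ask if they are willing to complete the post-test assessment". It mentions no debriefing, no referral and no recording of reasons.

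**Setting and monitoring.** Under section 24.1, baseline, sessions, post-test and follow-up "will take place outside of the lab online via Qualtrics". Section 18, headed "Provisions to Monitor the Data to Ensure the Safety of Subjects", contains only N/A.

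**Data and analysis.** Section 6.4 limits the data to demographics and self-report questionnaires. The list in section 6.2 includes the CES-D, GAD-7, SPIN and ED-15 but no measure of unwanted effects. Section 4.1 examines these scales for decreases. Section 17.1 compares the arms by baseline-adjusted regression and describes no harms or deterioration analysis.

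**The concern.** The protocol names a foreseeable unwanted effect, distress during exposure, and says others may appear. The planned flow of information and data takes little account of either. The one point at which clinical contacts are scheduled to be shown comes at the end of the last assessment, and someone who stops because of distress is among the people least likely to get there.

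The second issue is evidential. The reassurance in section 6.3 comes from people who had completed ETP, so it says nothing about those who stopped. According to section 3.1 that study had five sessions and undergraduate participants. This trial has a first session plus seven more and also recruits from the community. A randomised comparison with an active control is a good place to learn whether ETP makes some people worse, but the plan prespecifies nothing that would show it at the level of the individual.

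**Working it through.** The point is mainly textual, and the plan states no figure on it to reproduce.

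**Step 1: follow three participants through the text.**

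| Participant | Clinical numbers shown? | Other routes stated | Unwanted effects asked about? |
|---|---|---|---|
| Completes follow-up | Yes, in the debriefing form | Referral on request; staff contacts from consent; optional feedback e-mail | No; the e-mail asks for impressions and suggested changes |
| Withdraws formally | Not stated | Referral on request; staff contacts; invited to post-test | No; reasons for leaving are not mentioned |
| Stops silently | Not stated | Referral on request; staff contacts | No |

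In the last two rows every route before debriefing needs the participant to make contact or to disclose something.

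**Step 2: the interval before debriefing.** Post-test is on day 16, and follow-up is one month after post-test is completed (section 6.2). Taking a month as 28 to 30 days, 16 + 28 = 44 and 16 + 30 = 46. The form therefore appears about 44 to 46 days after baseline, roughly six and a half weeks.

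**Step 3: scale of early leaving.** Section 25.1 gives 68 needed and up to 80 recruited; sections 1.0 and 12.1 give 84.
- 80 − 68 = 12, and 12/80 = 15%.
- 84 − 68 = 16, and 16/84 = 19%.

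This is a recruitment margin for any reason across both arms. It is not a forecast of distressed participants. The 80 and the 84 disagree, but that does not affect this point.

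**Step 4: what the planned analysis can show.** The regression in section 17.1 would reveal a mean difference unfavourable to ETP on depression, anxiety, social anxiety or eating-disorder symptoms. It would not show how many individuals deteriorated, and it contains nothing on adverse events or reasons for stopping.

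**Step 5: why a worsening count needs a threshold.** Assume no true change, symmetric measurement noise and no ties. Half of participants would then score worse on any one scale. The share worse on at least one of four scales is 50% if the scales move together perfectly, and 1 − 0.5⁴ = 94% if they are independent. With 42 per arm that is 21 to 39 people from noise alone. Under a two-sided 5% reliable-change criterion, noise would flag 2.5% per scale, and at most 1 − 0.975⁴ = 9.6% on at least one scale if independent: about 1 to 4 of 42.

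**Step 6: what a harms table could exclude.** With no events in an arm, the one-sided 95% upper bound is 1 − 0.05^(1/n). This is 6.9% for n = 42 and 8.4% for n = 34. The table would be descriptive.

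**The case against.** The best defence is that the provisions are sparse but coherent. The phone numbers appear under the self-report heading of section 15.1, for people who want treatment once the study is over, so debriefing is a natural place for them. Distress during the study has its own provision, referral on request, with no time limit and no need to finish follow-up. Everyone has staff contact details, is warned of discomfort and may stop at any time. N/A in section 18 is consistent with a study rated minimal risk. Section 15.1 cites a separate suicide-risk procedure, and section 6.3 refers to data-collection materials in the ethics submission; neither is in the reviewed documents.

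Much of this stands, and it rules out three stronger readings that a reader might infer.

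- *That safeguards reach only people who finish follow-up or contact staff.* The warning, the right to stop and the staff contacts reach everyone. Online delivery does not exclude staff contact. Section 14.2 is silent on debriefing withdrawers and does not deny it to them.
- *That harms cannot be reported.* Section 17.1 already compares symptom means by arm, and worsening could be tabulated for anyone who returns questionnaires. What is missing is prespecification, an unwanted-effects item and reasons for drop-out.
- *That 12 to 16 distressed people would be missed.* The figure is a sample-size margin, and the documents give no rate of distress.

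The defence does not supply a stated route by which the existing referral list reaches someone who leaves early without asking. Nor does it supply any planned collection or analysis of unwanted effects.

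**Conclusion.** The point holds as a gap in information flow and in harms reporting. The documents do not show that participants are left without help. Referral numbers are scheduled about six and a half weeks after baseline, and no text carries them to people who leave before then. Unwanted effects, individual deterioration and distress-related drop-out have no systematic place in the data or the analysis. Sections 14.2, 15.1, 15.2, 18 and 24 need to be read against each other and reconciled.

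The importance is modest. The primary comparison is untouched, and the number affected is unknown; the 15% to 19% margin gives only an order of magnitude for early leaving. The conclusion assumes that the suicide-risk form, the survey materials and the removed consent pages do not already fill the gap, which could not be checked.

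**What to change.** 1. Reconcile sections 14.2, 15.1, 15.2, 18 and 24 so that the debriefing and referral list the sponsor has already written also reaches participants who withdraw or stop before follow-up. If the suicide-risk form or consent pages already cover this, a cross-reference is enough.
2. Add one unwanted-effects item to the existing post-test and follow-up surveys, in both arms.
3. Prespecify one descriptive table by arm giving the answers to that item, drop-out with reasons where given, and the number whose CES-D, GAD-7, SPIN or ED-15 score worsened from baseline by more than a threshold fixed in advance. A reliable-change criterion is one option; the documents give no reliability figures, so the sponsor would have to supply them.
4. State beside the table that it covers only people who return questionnaires. The new item cannot capture silent drop-outs, so the count of those without post-test data should be shown by arm.

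No treatment, stopping or crisis rule is proposed. The cost is some Qualtrics editing, one extra survey item and one table. The worsening counts use scales already collected. This is a cheap improvement.

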16.0 Potential Benefits to Subjects*

16.1 Potential individual benefits to subjects include decreasing their levels of perfectionism and/or decreasing levels of depression, anxiety, or eating disorder symptomatology.

17.0 Data Management* and Confidentiality

17.1 The data analysis plan begins with univariate and multivariate outliers being identified and transformed via Winsorization (Tukey & McLaughlin, 1963). Skewness and kurtosis will also be evaluated. Baseline differences between groups will then be identified using Chi-squared tests and independent samples t-tests. To analyze main outcomes, hierarchical intent-to-treat regression models will be used. These models will control for baseline variables. Multiple imputation using 20 iterations will be used to account for missing data. Effect sizes will be calculated using R^2 change values and were interpreted using Cohen's guidelines: small = .01, medium = .09, large = .25 (Cohen, 1988).

Secondary analyses include intervention response on measures of depression, trait anxiety, social anxiety, and eating disorder symptoms. Baseline values will be covaried in the regression models.

17.2 The data will be password protected on an encrypted computer only accessible by the research team. All identifying information will be removed and subjects will be referred to by ID numbers. Consent forms that include subjects' names will be stored on an encrypted computer only accessible to the research staff.

17.3 How data will be handled:

- Information in the data will include an ID number, demographics and all self-report assessment responses.
- Data will be stored in password-protected files on an encrypted computer that only the study team has access to.
- Data will be stored for a minimum of 4 years after study completion.
- Only members of the study team (i.e., those listed on the IRB submission) will have access to the data.
- The investigator is responsible for receipt or transmission of the data.
- If data needs to be transported, it will be done via password protected files on encrypted computers.

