4.0 Study Endpoints*

- 4.1 The primary endpoint will be scores from the Frost Multi-Dimensional Perfectionism Scale (FMPS)- Concern Over Mistakes Subscale at post-test. We will evaluate pre vs. post differences. The secondary endpoint will include scores from the Center for Epidemiological Studies Depression Scale (CES-D), the Generalized Anxiety Disorder-7 (GAD-7), the Social Phobia Inventory (SPIN), and the ED-15 to see if there are any decreases from pre to post assessment.
- 4.2 Additionally, we will evaluate post-test versus one month follow-up differences on the above stated measures.

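### Does Winsorizing outliers before the primary regression, with no stated cut-off and only R² change named as effect size, put the primary result at risk?

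*Combined protocol and SAP*

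**What the plan says.** Section 17.1 is the only analysis text in the document. Its first step is that "The data analysis plan begins with univariate and multivariate outliers being identified and transformed via Winsorization", supported by a literature citation. Skewness and kurtosis are then examined and baseline differences are tested. For the main comparison, "To analyze main outcomes, hierarchical intent-to-treat regression models will be used", controlling for baseline variables. On missing data, "Multiple imputation using 20 iterations will be used to account for missing data". On effect size, "Effect sizes will be calculated using R^2 change values", read against the benchmarks "small = .01, medium = .09, large = .25".

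The primary endpoint in section 4.1 is the FMPS "Concern Over Mistakes Subscale at post-test". Section 10.2 restricts entry on the same scale: "Subjects must be between the ages of 18 and 65 and score at least a 29 on the FMPS-CM". Section 12.1 gives the size: "84 subjects will be recruited, with 42 in the ETP group and 42 in the stress management group". Section 2.2 states a directional hypothesis, with lower perfectionism under the exposure-based intervention (ETP).

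The plan does not give an SD multiple, fence or percentile. It does not say whether the arms are pooled, which value changes when an outlier is multivariate, or whether Winsorizing comes before imputation. It does not promise a run on unmodified scores or a confidence interval.

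**The concern.** Winsorizing changes recorded values of the primary outcome. If the cut-off is chosen after the data are seen, an analyst could in principle choose the rule that gives the preferred answer, and a reader could not tell how much the result depends on the altered scores. An extreme low post-test score might be a careless answer in an unsupervised online survey (section 24.1). It might also be a strong responder, which is the effect the trial hopes to find. Pulling such scores in would weaken the estimate.

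The effect measure adds to the worry. R² change is the same for a benefit and a harm of equal size, is not in FMPS points, and is planned without an interval. At stake would be the size, and occasionally the significance, of the primary comparison.

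**Working it through.** **Inputs from the document.** 42 per arm (section 12.1); 34 per arm as the power-analysis size (section 25.1); entry at 29 or above (section 10.2); 20 imputations and baseline adjustment (section 17.1).

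**Assumed inputs.** Concern Over Mistakes range 9 to 45; baseline normal (mean 33, SD 5) cut to 29–45; slope of post-test on baseline 0.6; residual SD 4.5; rounded scores; arms pooled; baseline and post-test both Winsorized to the limit; then ANCOVA. Each effect scenario used 20,000 trials and each null scenario 40,000.

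**The plan's own figures.** The only computed figure is the total of 68 in section 25.1. It comes out exactly under an assumed f² of 0.15, alpha .05, 80% power and an omnibus test of two predictors, but it does not bear on this point. The R² benchmarks can be converted for 1:1 groups with d = 2√(R²/(1−R²)):
- .01: 2√(.01/.99) = 0.20
- .09: 2√(.09/.91) = 0.63
- .25: 2√(.25/.75) = 1.15

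These labels are therefore not labels for standardized mean differences. That affects reading, not analysis.

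**Effect of the rule on the estimate, 42 per arm.** Shrinkage = 1 − (Winsorized difference ÷ unmodified difference). In the responder column, ETP gains 1.5 points overall and 10–30% of that arm drop a further 12–15.

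| Rule | No post-test score altered (uniform 3 points) | Shrinkage, uniform 3 points | Shrinkage, strong responders |
|---|---|---|---|
| 3.29 SD | 98% of trials | 0.0% | 0.0–0.8% |
| 3 SD | 93% | 0.1% | 0.1–1.8% |
| 2.5 SD | about 51% | 0.5% | 1.3–5.2% |
| 1.5 IQR | 66% | 0.6% | 2.8–8.5% |
| 2 SD | 1% | 3.1% | 5.1–11.6% |

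The worst cell is a fall from 2.96 to 2.62 points. Power goes from .849 to .846 at worst for the uniform effect, and from .697 to .655 at worst with 10% strong responders. Where extremes are noise, a 2 SD rule raises power: .912 to .945 with t3 errors, and .625 to .677 with 8% careless responding.

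**False positives.** Under null scenarios each single rule gives .048–.051; a separate rerun gave about .046 under every rule. Taking the most favourable of six analyses (unmodified plus the five fences) gives .052–.057. The reason is structural: a pooled rule ignores arm labels, so under the null it treats both arms alike.

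**Change of verdict.** The p<.05 verdict differs somewhere among the six analyses in 0.6–7.0% of trials.

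**Smaller samples and missing data.** With 34 per arm and complete data, shrinkage is 0–11.3% and the verdict differs in 0.8–6.4%. With 8 of 42 per arm missing (42 − 34 = 8), Winsorizing first and then 20 imputations, shrinkage is 0–11.4%, type I error .047–.049, and the verdict differs in 1.0–6.6%.

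**Percentile rules.** A second simulation (residual SD 5, baseline mean 32 before truncation, 42 per arm, 3,000 trials) altered a fixed share of each tail.
- Uniform effect: 2.98 falls to 2.73 at 5% per tail (0.25/2.98 = 8.4%) and to 2.44 at 10% (0.54/2.98 = 18.1%).
- Benefit confined to 20% large responders: 2.94 falls to 2.51 (0.43/2.94 = 14.6%) and to 1.95 (0.99/2.94 = 33.7%). At 10% per tail, power goes from .528 to .399 and the verdict differs from the unmodified analysis in 13.5% of trials.

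**Sign and interval.** In a constructed data set of 68, adjusted differences of −3 and +3 give the same R² change (0.088) and the same standard error (1.123). R² change alone is therefore blind to direction. The same fit, however, gives the coefficient. With 68 − 3 = 65 degrees of freedom and critical t of 1.997, the half-width is 1.997 × 1.123 = 2.24, so the interval for −3 runs from −5.24 to −0.76. No further model is needed.

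**The case for a change.** The strongest case for a change is that the rule is open on the primary endpoint, that citing a method does not fix a cut-off, and that the remedy costs a few sentences and one extra model run. Percentile Winsorizing is not excluded, and there the effect is not small: about a third of the estimate in the worst responder case. The 0.6–7.0% range therefore does not bound every rule an analyst might use. By-arm and multivariate rules were not simulated.

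Several parts of this stand. The omissions are as described, the figures for fences apply only to the six analyses run, and a heavy percentile rule would visibly weaken a responder-driven effect.

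Three things limit it. First, section 17.1 has outliers identified and then transformed. That describes a detection fence more naturally than a rule altering a fixed share of scores whatever their values. Second, in the effect scenarios with strong responders the cost is a smaller estimate and some lost power, not a manufactured benefit; where extremes are noise, the step helps. Third, the claim that nearly all altered post-test scores would be low does not follow from the entry criterion, which limits baseline only. It rests on an assumed ceiling of 45 and an assumed post-test mean. The share under 3 or 3.29 SD is 91–100% on the main assumptions, but 77% and 86% under 3 SD in two runs where control scores also fall by 2 points.

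On R² change, naming one effect size does not prevent reporting the coefficient. The directional hypothesis in section 2.2 cannot be assessed without looking at its sign.

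**Conclusion.** No change to the plan follows. Winsorizing is a defensible robust choice, named in advance, and the missing cut-off is a detail that any conventional fence fills without disturbing the conclusion. With SD or interquartile fences, the primary difference shrinks by 0–3% for a uniform effect and by up to about 12% with assumed strong responders under a 2 SD rule. Type I error stays near its nominal level. A side-by-side run on unmodified scores would be an informative display, but it would not alter the primary result. The signed difference and its interval come from the regression already planned, so giving them beside R² change is ordinary reporting.

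The conclusion depends on the assumed score range, distributions, slope and residual SD; only the arm sizes, the entry score of 29 and the 20 imputations come from the document. It also takes the wording to mean a fence applied to pooled arms. A 10% per tail rule is the exception, at about 33% shrinkage in the responder case.
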